### ANNEX 3. LIST OF MEDICATION MEASURE DEFINITIONS

Name	Components
Corticosteroids	Betamethasone, *beclometasone (beclomethasone), cortisone acetate, dexamethasone, hydrocortisone, methylprednisolone, prednisolone, prednisone, triamcinolone, deflazacort, fludrocortisone
Short Acting Beta Agonist	Albuterol, metaproterenol, levalbuterol, pirbuterol, terbutaline
Short Acting Muscarinic Antagonist	Ipratropium
Long Acting Muscarinic Antagonist (LAMA)	Umeclidinium, glycopyrrolate, tiotropium, aclidinium, Incruse, Seebri, Spiriva, Tudorza
Long Acting Beta Agonist (LABA)	Indacaterol, arformoterol, formoterol, salmeterol, olodaterol, Arcapta, Atimos, Brovana, Perforomist, Serevent, Striverdi, Foradil
Inhaled Corticosteroids	Flunisolide, budesonide, mometasone, ciclesonide, fluticasone, beclomethasone, Aerobid, Aerospan, Alvesco, Armonair, Arnuity, Asmanex, Azmacort, Flixotide, Flovent, Pulmicort, Qvar
LAMA / LABA combination	indacaterol/glycopyrrolate, glycopyrrolate/formoterol, Utibron, Bevespi
LABA / ICS combination	Fluticasone/vilanterol, budesonide/formoterol, fluticasone/salmeterol, mometasone/formoterol, Advair, Symbicort, Breo, Dulera
LAMA / LABA / ICS combination	Fluticasone/umeclidinium/vilanterol, Trelegy
NSAIDs	Phenylbutazone, sulindac, tolmetin, diclofenac, etodolac, ketorolac, piroxicam, meloxicam, ibuprofen, naproxen, ketoprofen, fenoprofen, suprofen, flurbiprofen, oxaprozin, mefanamic acid, meclofenamic acid, celecoxib, rofecoxib, valdecoxib, nabumetone, glucosamine sulfate

Opioids	Morphine, hydromorphone, oxycodone, dihydrocodeine, fentanyl, pentazocine, buprenorphine, butorphanol, nalbuphine, tramadol, tapentadol, hydrocodone, codeine
Antihistamines/Antiallergic s	Diphenhydramine, clemastine, carboxamine, doxylamine, brompheniramine, dexchlorpheniramine, pheniramine, tripeptenamine, promethazine, thiethylperazine, cyclizine, chlorcyclizine, cetirizine, cyproheptadine, phenindamine, triprolidine, azatadine, astemizole, terfenadine, loratadine, ketotifen, azelastine, levocabastine, epinastine, fexofenadine, desloratadine, ephedrine, phenylephrine, oxymetazoline, xylometazoline, naphazoline, nedocromil

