Heart Failure	
1 Inpatient
 
Diagnosis Code (Any Position), ICD-9 is any of: { “428”, “428.0”, “428.1”, “428.2”, “428.20”, “428.21”, “428.22”, “428.23”, “428.3”, “428.30”, “428.31”, “428.32”, “428.33”, “428.4”, “428.40”, “428.41”, “428.42”, “428.43”, “428.9” }
 
Diagnosis Code (Any Position), ICD-10 is any of: { “I50”, “I50.9”, “I50.2”, “I50.20”, “I50.21”, “I50.22”, “I50.23”, “I50.3”, “I50.30”, “I50.31”, “I50.32”, “I50.33”, “I50.4”, “I50.40”, “I50.41”, “I50.42”, “I50.43” }

Hypertension	
1 Inpatient or 2 Outpatient (30 – 365 days apart)
 
Diagnosis Code (Any Position), ICD-9 is any of: { “401”, “401.0”, “401.1”, “401.9”, “402”, “402.0”, “402.00”, “402.1”, “402.10”, “402.9”, “402.90”, “403”, “403.0”, “403.00”, “403.01”, “403.1”, “403.10”, “403.11”, “403.9”, “403.90”, “403.91”, “404”, “404.0”, “404.00”, “404.01”, “404.02”, “404.03”, “404.1”, “404.10”, “404.11”, “404.12”, “404.13”, “404.9”, “404.90”, “404.91”, “404.92”, “404.93”, “405”, “405.0”, “405.01”, “405.09”, “405.1”, “405.11”, “405.19”, “405.9”, “405.91”, “405.99” }
 
Diagnosis Code (Any Position), ICD-10 is any of: { “I10”, “I11.9”, “I12.0”, “I12.9”, “I13.0”, “I13.10”, “I13.11”, “I13.2”, “I15.0”, “I15.8” }

Upper Respiratory Infection (with no sinusitis)	
1 Inpatient or 2 Outpatient (30 – 365 days apart)
 
Diagnosis Code (Any Position), ICD-9 is any of: { “034”, “034.0”, “034.1”, “460”, “461”, “461.0”, “461.1”, “461.2”, “461.3”, “461.8”, “461.9”, “462”, “463”, “464”, “464.0”, “464.00”, “464.01”, “464.1”, “464.10”, “464.11”, “464.2”, “464.20”, “464.21”, “464.3”, “464.30”, “464.31”, “464.4”, “464.5”, “464.50”, “464.51”, “465”, “465.0”, “465.8”, “465.9”, “487”, “487.1”, “487.8” }
 
Diagnosis Code (Any Position), ICD-10 is any of: { “J03.00”, “J03.01”, “A38”, “A38.8”, “A38.9”, “J00”, “J01”, “J01.9”, “J01.90”, “J01.8”, “J01.80”, “J01.0”, “J01.00”, “J01.01”, “J32.0”, “J01.1”, “J01.10”, “J01.11”, “J32.1”, “J01.2”, “J01.20”, “J01.21”, “J32.2”, “J01.3”, “J01.30”, “J01.31”, “J32.3”, “J02”, “J02.8”, “J02.9”, “J04”, “J04.0”, “J05”, “J05.0”, “J04.1”, “J04.10”, “J04.11”, “J04.2”, “J05.1”, “J05.10”, “J05.11”, “J04.3”, “J04.30”, “J04.31”, “J06”, “J06.9”, “J11.89”, “J11.8”, “J11.1”, “J11”, “J10.89”, “J10.8”, “J10.1”, “J10.00”, “J10.0”, “J10”, “J09.X2”, “J09.X9”, }

	“J09.X”, “J09” }

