Lower Respiratory Infection	
1 Inpatient or 2 Outpatient (30 – 365 days apart)
 
Diagnosis Code (Any Position), ICD-9 is any of: { “466”, “466.0”, “466.1”, “466.11”, “466.19” }
 
Diagnosis Code (Any Position), ICD-10 is any of: { “J20.9”, “J21.0”, “J21.8”, “J22” }

Cardiac Arrhythmias	
1 Inpatient or 1 Outpatient
 
Diagnosis Code (Principal), ICD-9 is any of: { “427”, “427.0”, “427.1”, “427.2”, “427.3”, “427.31”, “427.32”, “427.4”, “427.41”, “427.42”, “427.5”, “427.6”, “427.60”, “427.61”, “427.69”, “427.8”, “427.81”, “427.89”, “427.9” }
 
Diagnosis Code (Position 1), ICD-10 is any of: { “I46.9”, “I47.1”, “I47.2”, “I47.9”, “I48.91”, “I48.92”, “I49.01”, “I49.02”, “I49.1”, “I49.3”, “I49.40”, “I49.49”, “I49.5”, “I49.8”, “I49.9”, “R00.1” }

Cerebrovascular Disease	
1 Inpatient
 
Diagnosis Code (Any Position), ICD-9 is any of: { “430”, “431”, “432”, “432.0”, “432.1”, “432.9”, “433”, “433.0”, “433.01”, “433.1”, “433.11”, “433.2”, “433.21”, “433.3”, “433.31”, “433.8”, “433.81”, “433.9”, “433.91”, “434”, “434.0”, “434.01”, “434.1”, “434.11”, “434.9”, “434.90”, “434.91”, “435”, “435.8”, “435.9”, “436” }
 
Diagnosis Code (Any Position), ICD-10 is any of: { “G45”, “G45.8”, “G45.9”, “I60”, “I60.0”, “I60.00”, “I60.01”, “I60.02”, “I60.1”, “I60.10”, “I60.11”, “I60.12”, “I60.2”, “I60.20”, “I60.21”, “I60.22”, “I60.3”, “I60.30”, “I60.31”, “I60.32”, “I60.4”, “I60.5”, “I60.50”, “I60.51”, “I60.52”, “I60.6”, “I60.7”, “I60.8”, “I60.9”, “I61”, “I61.0”, “I61.1”, “I61.2”, “I61.3”, “I61.4”, “I61.5”, “I61.6”, “I61.8”, “I61.9”, “I62”, “I62.0”, “I62.00”, “I62.01”, “I62.02”, “I62.03”, “I62.1”, “I62.9”, “I63”, “I63.0”, “I63.00”, “I63.01”, “I63.011”, “I63.012”, “I63.019”, “I63.02”, “I63.03”, “I63.031”, “I63.032”, “I63.039”, “I63.09”, “I63.1”, “I63.10”, “I63.11”, “I63.111”, “I63.112”, “I63.119”, “I63.12”, “I63.13”, “I63.131”, “I63.132”, “I63.139”, “I63.19”, “I63.2”, “I63.20”, “I63.21”, “I63.211”, “I63.212”, “I63.219”, “I63.22”, “I63.23”, “I63.231”, “I63.232”, “I63.239”, “I63.29”, “I63.3”, “I63.30”, “I63.31”, “I63.311”, “I63.312”, “I63.319”, “I63.32”, “I63.321”, “I63.322”, “I63.329”, “I63.33”, “I63.331”, “I63.332”, “I63.339”, “I63.34”, “I63.341”, “I63.342”, “I63.349”, “I63.39”, “I63.4”, “I63.40”, “I63.41”, “I63.411”, “I63.412”, “I63.419”, “I63.42”, “I63.421”, “I63.422”, “I63.423” }

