Dementia	
1 Inpatient or 2 Outpatient (30 – 365 days apart)
 
Diagnosis Code (Any Position), ICD-9 is any of: { “290.0”, “290.1”, “290.10”, “290.11”, “290.12”, “290.13”, “290.2”, “290.20”, “290.21”, “290.3”, “290.4”, “290.40”, “290.41”, “290.42”, “290.43”, “291.2”, “292.82”, “294.0”, “294.1”, “294.10”, “294.11”, “294.8”, “331.0”, “331.1”, “331.11”, “331.19”, “331.2”, “331.7”, “331.8”, “331.81”, “331.82”, “331.83”, “331.89”, “331.9”, “797” }
 
Diagnosis Code (Any Position), ICD-10 is any of: { “F01.50”, “F01.51”, “F02.80”, “F02.81”, “F03.90”, “F04”, “F05”, “F06.0”, “F06.8”, “F10.27”, “F19.97”, “G30.9”, “G31.01”, “G31.09”, “G31.1”, “G31.83”, “G31.84”, “G31.89”, “G31.9”, “G93.7”, “G94”, “R41.81”, “F32”, “F32.8”, “F33”, “F33.8” }
 
Generic Name is any of: { “DONEPEZIL HCL”, “GALANTAMINE HBR”, “RIVASTIGMINE”, “MEMANTINE HCL” }

Depression	
1 Inpatient or 2 Outpatient (30 – 365 days apart)
 
Diagnosis Code (Any Position), ICD-9 is any of: { “296.2”, “296.20”, “296.21”, “296.22”, “296.23”, “296.24”, “296.25”, “296.26”, “296.3”, “296.30”, “296.31”, “296.32”, “296.33”, “296.34”, “296.35”, “296.36”, “298.0”, “300.4”, “309.0”, “309.1”, “309.28”, “311” }
 
Diagnosis Code (Any Position), ICD-10 is any of: { “F32.0”, “F32.1”, “F32.2”, “F32.3”, “F32.4”, “F32.5”, “F32.9”, “F33.0”, “F33.1”, “F33.2”, “F33.3”, “F33.41”, “F33.42”, “F33.9”, “F34.1”, “F43.21”, “F43.23” }

Osteoporosis	1 Inpatient or 2 Outpatient (30 – 365 days apart)

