Charlson-Deyo Comorbidity Index	
This measure computes a score by summing over the following components:
 
 
· If the event Acute Myocardial Infarction Occurs within 180 days, set the score to 1.0 Otherwise, set the score to 0.0
 
· If the event Heart Failure Occurs within 180 days, set the score to 1.0 Otherwise, set the score to 0.0
 
· If the event Peripheral Vascular Disease Occurs within 180 days, set the score to 1.0 Otherwise, set the score to 0.0
 
· If the event Cerebrovascular Disease Occurs within 180 days, set the score to 1.0 Otherwise, set the score to 0.0
 
· If the event Dementia Occurs within 180 days, set the score to 1.0 Otherwise, set the score to 0.0
 
· If the event Chronic Obstructive Pulmonary Disease Occurs within 180 days, set the score to 1.0 Otherwise, set the score to 0.0
 
· If the event Rheumatologic Disease Occurs within 180 days, set the score to 1.0 Otherwise, set the score to 0.0
 
· If the event Peptic Ulcer Disease Occurs within 180 days, set the score to 1.0 Otherwise, set the score to 0.0
 
· If the event Hemiplegia or Paraplegia Occurs within 180 days, set the score to 2.0 Otherwise, set the score to 0.0
 
· If the event Renal Disease Occurs within 180 days, set the score to 2.0 Otherwise, set the score to 0.0
 
· If the event HIV/AIDS Occurs within 180 days, set the score to 6.0 Otherwise, set the score to 0.0
 
· For the measure Cancer use the value of the measure as the score multiplied by weight 1.0 If the value is missing, set the score to 0.0
 
· For the measure Diabetes use the value of the measure as the score multiplied by weight 1.0 If the value is missing, set the score to 0.0
 
· For the measure Liver Disease use the value of the measure as the score multiplied by weight 1.0 If the value is missing, set the score to 0.0
 

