Rheumatologic Disease	1 Inpatient or 2 Outpatient (30 – 365 days apart)  Diagnosis Code (Any Position), ICD-9 is any of: { “135”, “183.0”, “274.9”, “275.49”, “279.49”, “443.0”, “448.9”, “530.5”, “555.9”, “571.42”, “571.6”, “576.1”, “579.0”, “696.0”, “696.1”, “710.0”, “710.1”, “710.2”, “710.3”, “710.9”, “711.90”, “712.19”, “714.0”, “714.30”, “715.09”, “715.11”, “715.12”, “715.13”, “715.14”, “715.15”, “715.17”, “715.18”, “715.96”, “719.42”, “719.44”, “719.45”, “719.47”, “719.49”, “720.0”, “721.90”, “725”, “729.1”, “729.5”, “795.79” }  Diagnosis Code (Any Position), ICD-10 is any of: { “D59.0”, “D59.1”, “D86.9”, “D89.89”, “E83.59”, “I73.00”, “I73.01”, “I78.9”, “K22.4”, “K50.90”, “K74.3”, “K74.4”, “K74.5”, “K75.4”, “K83.0”, “K90.0”, “L40.0”, “L40.1”, “L40.2”, “L40.50”, “L40.54”, “L40.59”, “L40.8”, “M00.9”, “M06.9”, “M08.00”, “M10.9”, “M11.9”, “M15.0”, “M16.0”, “M16.10”, “M16.11”, “M16.12”, “M17.9”, “M19.019”, “M19.029”, “M19.039”, “M19.049”, “M19.079”, “M19.91”, “M25.50”, “M25.529”, “M25.559”, “M25.579”, “M32.10”, “M33.90”, “M34.0”, “M34.1”, “M34.2”, “M34.81”, “M34.82”, “M34.83”, “M34.89”, “M34.9”, “M35.00”, “M35.01”, “M35.02”, “M35.03”, “M35.04”, “M35.09”, “M35.3”, “M35.9”, “M45.9”, “M47.819”, “M60.9”, “M76.0”, “M76.11”, “M76.12”, “M76.8”, “M76.9”, “M79”, “M79.1”, “M79.609”, “M79.646” }

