Type 1 or Type 2 Diabetes with Complications	
1 Inpatient or 2 Outpatient (30 – 365 days apart)
 
Diagnosis Code (Any Position), ICD-9 is any of: { “250.4”, “250.40”, “250.41”, “250.42”, “250.43”, “250.5”, “250.50”, “250.51”, “250.52”, “250.53”, “250.6”, “250.60”, “250.61”, “250.62”, “250.63”, “250.3”, “250.30”, “250.31”, “250.32”, “250.33” }
 
Diagnosis Code (Any Position), ICD-10 is any of: { “E10.2”, “E10.21”, “E10.22”, “E10.29”, “E10.3”, “E10.31”, “E10.311”, “E10.319”, “E10.32”, “E10.321”, “E10.329”, “E10.33”, “E10.331”, “E10.339”, “E10.34”, “E10.341”, “E10.349”, “E10.35”, “E10.351”, “E10.359”, “E10.36”, “E10.39”, “E10.4”, “E10.40”, “E10.41”, “E10.42”, “E10.43”, “E10.44”, “E10.49”, “E10.5”, “E11.2”, “E11.21”, “E11.22”, “E11.29”, “E11.3”, “E11.31”, “E11.311”, “E11.319”, “E11.32”, “E11.321”, “E11.329”, “E11.33”, “E11.331”, “E11.339”, “E11.34”, “E11.341”, “E11.349”, “E11.35”, “E11.351”, “E11.359”, “E11.36”, “E11.39”, “E11.4”, “E11.40”, “E11.41”, “E11.42”, “E11.43”, “E11.44”, “E11.49”, “E11.5”, “E13.4”, “E13.40”, “E13.41”, “E13.42”, “E13.43”, “E13.44”, “E13.49”, “E13.5” }

Mild Liver Disease	
1 Inpatient or 2 Outpatient (30 – 365 days apart)
 
Diagnosis Code (Any Position), ICD-9 is any of: { “571.2”, “571.4”, “571.40”, “571.41”, “571.42”, “571.49”, “571.5”, “571.6” }
 
Diagnosis Code (Any Position), ICD-10 is any of: { “B18.0”, “B18.1”, “B18.2”, “B18.8”, “B18.9”, “K70.0”, “K70.1”, “K70.10”, “K70.11”, “K70.2”, “K70.3”, “K70.9”, “K71.3”, “K71.4”, “K71.5”, “K71.7”, “K73.0”, “K73.1”, “K73.2”, “K73.8”, “K73.9”, “K74.0”, “K74.1”, “K74.2”, “K74.3”, “K74.4”, “K74.5”, “K74.6”, “K74.60”, “K74.69”, “K76.0”, “K76.2”, “K76.3”, “K76.4”, “K76.8”, “K76.9”, “Z94.4” }

Moderate/Severe Liver Disease	
1 Inpatient or 2 Outpatient (30 – 365 days apart)
 
Diagnosis Code (Any Position), ICD-9 is any of: { “456.0”, “456.1”, “456.2”, “456.20”, “456.21”, “572.2”, “572.3”, “572.4”, “572.8” }
 
Diagnosis Code (Any Position), ICD-10 is any of: { “I85.0”, “I86.4”, “K70.4”, “K71.1”, “K72.1”, “K72.9”, “K76.5”, “K76.6”, “K76.7” }

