	
“342.11”, “342.12”, “342.8”, “342.80”, “342.81”, “342.82”, “342.9”, “342.90”, “342.91”, “342.92”, “344.1” }
 
Diagnosis Code (Any Position), ICD-10 is any of: { “G81.00”, “G81.01”, “G81.02”, “G81.03”, “G81.04”, “G81.10”, “G81.11”, “G81.12”, “G81.13”, “G81.14”, “G81.90”, “G81.91”, “G81.92”, “G81.93”, “G81.94”, “G82.20”, “G81”, “G81.9”, “I69.05”, “I69.051”, “I69.052”, “I69.053”, “I69.054”, “I69.059”, “I69.15”, “I69.151”, “I69.152”, “I69.153”, “I69.154”, “I69.159”, “I69.25”, “I69.251”, “I69.252”, “I69.253”, “I69.254”, “I69.259”, “I69.35”, “I69.351”, “I69.352”, “I69.353”, “I69.354”, “I69.359”, “I69.85”, “I69.851”, “I69.852”, “I69.853”, “I69.854”, “I69.859”, “I69.95”, “I69.951”, “I69.952”, “I69.953”, “I69.954”, “I69.959”, “G81.0”, “G81.1”, “G82.2”, “G82”, “G82.21”, “G82.22”, “G04.1”, “G11.4” }

	Lifestyle
Smoking-related claim	
1 Inpatient or 1 Outpatient
 
Diagnosis Code (Any Position), ICD-9 is any of: { “305.1”, “V15.82”, “989.84”, “649.0x” }
 
Diagnosis Code (Any Position), ICD-10 is any of: { “F17.2”, “T65.2”, “Z71.6”, “O99.33”, “O99.330”, “O99.331”, “O99.332”, “O99.333”, “O99.334”, “O99.335”, “Z72.0”, “Z81.2” }
 
Procedure Code (Any Position), CPT and HCPC is any of: { “99406”, “99407”, “G0436”, “G0437”, “G9016”, “S9453”, “S4995”, “G9276”, “G9458”, “1034F”, “4004F”, “4001F” }

Vaccination for Influenza/Pneumococcus	
1 Inpatient Service or 1 Outpatient
 
Procedure Code (Position 1), CPT and HCPC is any of: { “4040F”, “90630”, “90653”, “90654”, “90655”, “90656”, “90657”, “90658”, “90659”, “90660”, “90661”, “90662”, “90663”, “90664”, “90665”, “90666”, “90667”, “90668”, “90669”, “90670”, “90672”, “90673”, “90685”, “90686”, “90687”, “90688”, “90732”, “G0008”, “G0009”, “G0919”, “G8108”, “G8115”, “G8864”, “G9279”, “Q0034”, “Q2033”, “Q2034”, “Q2035”, “Q2036”, “Q2037”, “Q2038”, “Q2039”, “S0195” }

Respiratory Function Procedures/Tests	
Pulmonary function tests	1 Inpatient or 1 Outpatient  Procedure Code (Any Position), CPT and HCPC is any of: { “3038F”, “94010”, “94014”, “94015”, “94060”, “94621”, “94720”, “94725”, “94726”, “94727”, “94728”, “94729”, “94750”, “94770”, “94799” }  Procedure Code (Any Position), ICD-9 is any of: { “89.37” }  Procedure Code (Any Position), ICD-10 is any of: { “4A0971Z”, “4A0981Z”, “4A09X1Z”, “4A1971Z”, “4A19X1Z” }

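### Several Annex 4 code lists conflict with one another, and one Annex 3 row lacks a route, so some covariates and Table 2 rows are misclassified if applied as printed

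*Combined protocol and SAP*

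**What the plan says.** Annex 4 defines each comorbidity by a code list plus a claim-count rule. For most of the rows discussed here the rule is one inpatient claim, or two outpatient claims 30 to 365 days apart.

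- **Dementia** ends its ICD-10 list with "F32”, “F32.8”, “F33”, “F33.8". The Charlson row then says "If the event Dementia Occurs within 180 days, set the score to 1.0".
- **Rheumatologic Disease** opens its ICD-9 list with "135”, “183.0”, “274.9" and also carries 571.42, 571.6 and K74.3-K74.5. **Mild Liver Disease** ends its ICD-9 list with "571.42”, “571.49”, “571.5”, “571.6" and also carries K74.3-K74.5.
- One row is labelled "Upper Respiratory Infection (with no sinusitis" and contains J32.0-J32.3.
- **Type 2 Diabetes** gives a selection of E11 codes; the row for diabetes with complications gives a different selection.
- In Annex 3 a row headed Corticosteroids begins "Betamethasone, *beclometasone (beclomethasone), cortisone acetate" and names no route. Section 9.3.3 calls the covariate Oral Corticosteroids.
- The **smoking** row begins its ICD-10 list with "F17.2”, “T65.2”, “Z71.6", without wildcards.

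Section 9.2.2 (Matched Cohort) puts all Section 9.3.3 covariates except the Charlson components into the propensity model. Describing new users before and after matching is a secondary objective (Section 8), reported in Table 2 of Annex 5.

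**The concern.** A code that the annex itself treats as one condition should not, without explanation, define another. Where it does, the prevalence in Table 2 is not the prevalence of the condition named in the row.

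The errors reach the primary analysis by two routes. Dementia and Rheumatologic Disease are Charlson components, so they enter the propensity model and the multivariable models through the score. Depression, upper respiratory infection, oral steroid use and smoking enter directly. If these variables are wrongly built, the match balances something other than what the balance tables claim.

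**Working it through.** There is no planned figure to reproduce. The check compares the printed lists by exact code and traces each affected measure to where it is used.

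**1. Dementia and Depression.** Depression holds F32.0-F32.5 and F32.9 (7 codes) and F33.0-F33.3, F33.41, F33.42 and F33.9 (7 codes), 14 in all. Dementia holds F32, F32.8, F33 and F33.8. The two lists share no code: the four sit in the wrong row and are absent from the right one. Dementia is over-counted and Depression under-counted.

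**2. Rheumatologic Disease.** Shared with All Cancers: 183.0. Shared with Mild Liver Disease: 571.42, 571.6, K74.3, K74.4 and K74.5.

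**3. Upper Respiratory Infection.** Shared with Chronic Sinusitis: J32.0, J32.1, J32.2 and J32.3. The row also carries the J01 and ICD-9 461 blocks, which are acute sinusitis codes, so its label would still be contradicted with J32 removed.

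**4. Diabetes.** E11.22 and E11.42 are in the complications list but not in Type 2 Diabetes. A patient identified only by one of them has diabetes with complications but not type 2 diabetes in Table 2. Code 250.3 stands in both the with- and without-complications lists, while 250.30-250.33 stand only in the former.

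**5. Oral steroids.** Corticosteroids is the only Annex 3 row that can define the covariate. It gives no route and shares beclomethasone with the inhaled row.

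**6. Matching rule.** None is stated. Wildcards appear in places (R06.0*, O98.7*, and 491.* in Section 9.2.2), and the smoking row spells out O99.330-O99.335 beside O99.33, which suggests exact matching. If so, F17.2, T65.2 and Z71.6 miss any longer code. Under prefix matching those three are sufficient, but bare F32 and F33 would then draw all 14 Depression codes into Dementia, and 250.3 in the without-complications list would draw in 250.30-250.33.

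**Effect on the Charlson score, per patient.** Dementia and Rheumatologic Disease each score 0 or 1.
- Qualifies for Dementia only through the four codes: 1 as printed, 0 after correction. With COPD also scoring 1 and nothing else, the total is 1 + 1 = 2 instead of 1, which crosses a Table 2 category.
- Qualifies only through 571.42, 571.6 or K74.3-K74.5: 1 + the liver value as printed, the liver value alone after correction. This holds only if the Charlson Liver Disease measure uses the Mild Liver list.
- Qualifies only through 183.0: 1 + the cancer value as printed, the cancer value alone after correction. This holds only if the Charlson Cancer measure uses the All Cancers list.
- Qualifies through any other listed code as well: no change in that component.

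**Effect on the cohort.** The documents give no code frequencies. As an assumption only, suppose 0.5% to 5% of patients gain one point wrongly. The mean score rises by 0.005 to 0.05. In patients this is 3,889 × 0.005 = 19 to 3,889 × 0.05 = 194 olodaterol/tiotropium users, and 10,862 × 0.005 = 54 to 10,862 × 0.05 = 543 umeclidinium/vilanterol users.

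**The case against.** The strongest reply is that this is housekeeping. Section 9.12 plans a medical review of code lists before implementation, and Section 9.8 adds a second-analyst check and lets definitions be modified. That stands as a safeguard, but it corrects none of the printed lists. Section 6 planned implementation from 01 March 2019, the annexes are dated 19 April 2019 and the protocol 22 November 2019, and the conflicts are still there. Section 9.8 also requires changes to be documented by amendment.

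Some overlap may be deliberate. F43.23 under both Anxiety and Depression is plausible, and Rheumatologic Disease is a broad list. That is a reason to state the intention. It does not explain sinusitis codes under a label that excludes sinusitis. Some lists may also come from validated algorithms, which cannot be told from the text.

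A reader might infer more than the documents support:
- **Every carrier of a misplaced code gains a Charlson point or is miscounted.** The components are capped at 1, claim-count rules apply, and patients who qualify otherwise are unaffected.
- **One diagnosis certainly scores twice.** Annex 4 does not say which lists feed the Charlson Cancer and Liver Disease measures.
- **Beclomethasone should be dropped as an inhaled drug misfiled under oral steroids.** The row is not headed oral, the ingredient carries an asterisk whose footnote is not in the available text, and route can separate the classes. Only the missing route is a defect.
- **Lower Respiratory Infection, with "J20.9”, “J21.0”, “J21.8”, “J22", contradicts the J20.0-J20.9 range elsewhere.** That range belongs to a different measure, hospitalisation by principal diagnosis. Widening the list is a preference.
- **The smoking list fails outright.** That depends on the unstated matching rule.

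**Conclusion.** The point holds as an internal inconsistency that misclassifies patients if the lists are run as printed. It rests on the printed text for the dementia, rheumatologic, sinusitis and diabetes conflicts, on the missing route for oral steroids, and on the missing matching rule for smoking.

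Only the dementia and rheumatologic errors can be traced into the Charlson score. The construction of the Charlson Diabetes measure is not shown, so no path to the score can be shown for the diabetes items. The remaining items affect their own covariates and Table 2 rows.

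The size cannot be derived. A reader might infer a materially biased primary hazard ratio, but nothing in the documents supports that: the same lists apply to both groups, each error touches only patients who qualify through the affected codes, and the bias is probably small. This is a minor point. The gain is correct Table 2 prevalences and correctly defined matching covariates.

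**What to change.** Amend Annexes 3 and 4:

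1. Move F32, F32.8, F33 and F33.8 from Dementia to Depression.
2. Remove 183.0, 571.42, 571.6 and K74.3-K74.5 from Rheumatologic Disease, treating K75.4 consistently with 571.42, or state that the overlap is intended. Name the lists that feed the Charlson Cancer and Liver Disease measures.
3. Remove J32.0-J32.3 from Upper Respiratory Infection, and either remove the J01 and 461 codes or relabel the row.
4. Use the full E11 block for Type 2 Diabetes and keep 250.3 in one diabetes list only.
5. Restrict the Oral Corticosteroids covariate to oral formulations.
6. State whether codes match exactly or by prefix. If exactly, add wildcards to F17.2, T65.2 and Z71.6.

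Before programming, the cost is an edit and a review that Section 9.12 already plans. If the measures are already built, the affected variables, the Charlson score, the propensity model and the match must be rerun. Where a list comes from a validated algorithm, editing it departs from the validated form. In that case, cite the source and explain the overlap or the change.
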